1. Focal echogenic lesion in carotid bifurcation (15 mm proximally to flow divider and 15 mm distally)
2. The lesion is present (interferes) in the posterior wall
3. Echogenicity of the lesion is higher than intraluminal blood
4. Maximal length of lesions 3.0 mm
5. Minimal intraluminal prominence (width) 2.0 mm
6. In longitudinal view: Shape of lesion is shelf-like nor valve-like, triangular with the sharpest angle proximally with the blood flow direction
7. In transversal view: Transversal linear defect with echogenic surface projecting in the arterial lumen (the shape should be nest-like)
8. Hemodynamic signature: focal flow separation/recirculation or color aliasing immediately distal to the shelf without proportionate atherosclerotic plaque; spectral Doppler may be normal or show subtle focal acceleration without classic stenosis criteria.

Exclusion criteria:

1. The length is greater than the width
2. Visible only in transversal and not longitudinal view
3. Presence of carotid plaque (Mannheim consensus) in the posterior wall

Suspected carotid web:*Inclusion criteria:*

1. Focal echogenic lesion in carotid bifurcation (15 mm proximally to flow divider and 15 mm distally)
2. Minimal intraluminal prominence (width) 1.5 mm
3. One out of these criteria:
 - a. In longitudinal view: Shape of lesion is shelf-like nor valve-like, triangular with the sharpest angle proximally with the blood flow direction
 - b. In transversal view: Transversal linear defect with echogenic surface projecting in the arterial lumen (the shape should be nest-like)

Exclusion criteria:

1. Presence of carotid plaque (Mannheim consensus) in the posterior wall

Differential sonographic features to record: typical plaque (echogenic/heterogeneous with surface calcification), carotid diaphragm, dissection flap (mobile, intramural hematoma), carotid web with superimposed thrombus.

7) Sonographic Case Definition of Carotid Web

Required equipment/settings (if specified in your criteria):

- Probe / frequency: 5-14 MHz
- Settings: MI 1.6, 37 fps, Q scan, dynamic range 70
- Patient position: supine position, slight neck extension/contralateral head rotation

Diagnostic categories (tick all that apply):

- Definite CaW — must meet morphology, location, hemodynamics criteria and exclusions ruled out (plaque, dissection, diaphragm, artifact).
- Probable CaW — meets some morphology criteria and exclusions ruled out (plaque, dissection, diaphragm, artifact).

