- Not CaW — meets no criteria for CaW.

Morphologic measurements (standardized):

- Web thickness (mm): ____ (measured at ____)
- Web length/projection into lumen (mm): ____
- Projection angle (°) relative to vessel wall: ____
- Distance from flow divider (mm): ____
- Side: left / right / bilateral

Hemodynamic signatures (as per your thresholds):

- Color Doppler recirculation/aliasing: present / absent (criteria: ____)
- Spectral Doppler acceleration: PSV ____ m/s (cutoff: ____); ICA/CCA ratio cutoff: ____
- Microflow imaging pattern: ____

Differential exclusion checklist (define image features to rule out):

- Atherosclerotic plaque: ____
- Dissection flap/intramural hematoma: ____
- Carotid diaphragm/other membranes: ____
- Artifact (reverberation, blooming): ____

Image acquisition minimums (per side):

- Transverse cine (≥ 3 cycles) focused on bulb/ICA origin
- Longitudinal cine in ≥ 2 insonation planes (lat & post-lat)
- Still frames (B-mode \pm color) with calipers for all measurements
- Spectral Doppler waveforms (CCA, bulb, proximal ICA) with angle correction $\leq 60^\circ$

Quality grading (apply your rules):

- Grade 1 (excellent) / 2 (diagnostic) / 3 (limited) — use only Grades 1–2 in primary analysis; Grade 3 in sensitivity analysis.

Reader guidance & adjudication using your criteria:

- Two blinded readers score Definite/Probable/Possible/Not CaW; discrepancies resolved by third reader under the same rubric.

- 10% repeat reads for κ /ICC.

CRF add-ons (pre-wired to your criteria)

- Checkboxes for each criterion element (present/absent/not evaluable).
- Auto-calculated category (Definite/Probable/Possible/Not CaW) based on boxes ticked.
- Mandatory image IDs linked to each measurement.

8) Training, Blinding, and Adjudication

- Sonographers undergo a standardized training module with exemplar images and checklists.
- **Blinding:** Operators are blinded to participant clinical data except age/sex; central readers (two expert neurosonologists) are blinded to site and each other.
- **Adjudication:** Disagreements (probable/possible/absent) resolved by a third senior reader.
- **Reliability:** 10% random sample re-read for inter-observer agreement (Cohen's κ for categorical calls; ICC for continuous measures).

9) Data Collection

- **Demographics:** age, sex, ethnicity (optional), height/weight.

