- **Vascular risk factors:** smoking status, BP at visit, lipid profile if available, personal history of stroke/TIA/migraine, OCP use (females), recreational drugs, connective tissue disease/FMD history.
- **Ultrasound fields:** laterality; CaW category (absent/possible/probable), web dimensions (length, thickness, projection angle—estimate), distance from flow divider, presence of superimposed thrombus, plaque descriptors, standard velocities (CCA, bulb, ICA), ICA/CCA PSV ratio, EDV.
- **Imaging quality scores** and reasons for non-diagnostic studies.

10) Validation Substudy

- Participants with definite or possible CaW on DUS plus 1:2 matched DUS-negative controls (matched by age/sex/site) will invited for CTA within 4 weeks to evaluate concordance (index test: DUS; reference standard: CTA with thin-slice oblique sagittal reconstructions). Outcome: sensitivity/specificity and positive predictive value of DUS criteria. (CTA descriptions of CaW as thin, shelf-like posterior bulb defects guide the reference call.)

11) Outcomes

- **Primary:** Point prevalence of **probable CaW** (participants with ≥ 1 carotid web / all with diagnostic scans), with 95% CI adjusted for sampling design.
- **Secondary:**
 - Prevalence including **possible + probable** (sensitivity analysis).
 - Distribution by side (left/right/bilateral).
 - Association between CaW and sex, smoking, BP, OCP use (exploratory).
 - Inter-observer agreement metrics.
 - In validation substudy: DUS diagnostic accuracy vs CTA.

12) Statistical Analysis Plan

- **Weighting:** Apply sampling weights for cluster/strata to estimate population prevalence; robust SEs (Taylor linearization) or survey-design GLMs.
- **Descriptives:** Means/SDs or medians/IQRs; counts/% with 95% CIs.
- **Primary analysis:** Weighted prevalence and **exact (Clopper–Pearson) or Wilson** CIs for rare events; compare strata with Rao–Scott χ^2 .
- **Regression (exploratory):** Survey-weighted Poisson (log link, robust variance) for prevalence ratios of CaW vs candidate covariates.
- **Reliability:** Cohen’s κ with 95% CI (categorical), ICC(2,1) for continuous measures.
- **Missing data:** Report flow; use complete-case for primary prevalence; multiple imputation for covariate analyses if $>5\%$ missing.

- **Sensitivity analyses:** (i) include **possible** CaW as positive; (ii) restrict to scans with top quality scores; (iii) per-reader estimates.

13) Bias Minimization & Quality Control

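### The two Section 7 texts draw the line between web and no web in different places, and the rules for Probable and Not CaW leave some lesions with contradictory calls or no defined category

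*Protocol*

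**What the plan says.** The first Section 7 (Sonographic Definition) has two tiers. Definite includes "Minimal intraluminal prominence (width) 2.0 mm". Suspected includes "Minimal intraluminal prominence (width) 1.5 mm", a location in the bifurcation, and either the longitudinal or the transverse shape criterion. The only exclusion listed for Suspected is plaque in the posterior wall.

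The second Section 7 (Sonographic Case Definition, Diagnostic categories) has three. The top tier, Definite, asks for shape, site and flow findings together, once the mimics have been excluded. The middle tier is worded "Probable CaW — meets some morphology criteria and exclusions ruled out (plaque, dissection, diaphragm, artifact". That rule gives neither a count of criteria nor a size limit. A negative call has its own rule, which is "Not CaW — meets no criteria for CaW".

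The reader guidance and the CRF add-ons in the same section use four levels, adding Possible, which is defined nowhere. The CRF has a box for each criterion element and derives the category from the boxes ticked.

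Sections 8, 9, 11 and 12 use a probable/possible scale. Section 11 makes the prevalence of probable CaW the primary outcome, over all participants with a diagnostic scan. Section 12 counts possible CaW as positive in a sensitivity analysis.

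**The concern.** A prevalence study depends on its case definition. Here two texts in the same protocol can give opposite calls for the same lesion, and the tier affected is the one named in the primary outcome. The negative category is also not the complement of the positive ones. It requires that no criterion at all is met, and several criteria are unspecific, for example "Echogenicity of the lesion is higher than intraluminal blood". A lesion can therefore be too weak or too plainly something else to be a web, and still not qualify as Not CaW.

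The same category feeds the inter-observer kappa and the choice of DUS-negative controls for the CTA substudy. An unclear boundary affects those as well.

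**Working it through.** **1. The plan's own figure.** Section 5 uses p = 0.02, d = 0.01 and Z = 1.96. n = 1.96² × 0.02 × 0.98 / 0.01² = 752.95, rounded up to 753. This reproduces. Expected cases: 753 × 0.02 = 15.06, about 15.

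**2. The rules applied literally.**

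| Lesion | First Section 7, Suspected | Second Section 7 |
|---|---|---|
| 1.0 mm shelf-shaped lesion, posterior wall of the bulb, exclusions ruled out | Rejected: 1.0 mm is below 1.5 mm | Probable (a shape criterion is met); cannot be Not CaW |
| Plaque in the posterior wall | Excluded | Meets location and echogenicity, so not Not CaW; exclusion present, so neither Probable nor Definite |
| Diaphragm or dissection flap in the bulb | Not a listed exclusion, only a feature to record | As for plaque |
| Lesion-free wall | Not met | Not CaW |

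The protocol expects such non-web lesions: "Differential sonographic features to record: typical plaque (echogenic/heterogeneous with surface calcification), carotid diaphragm, dissection flap (mobile, intramural hematoma"). For them the only remaining level is Possible.

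**3. Dependence on the labels, for the 1.0 mm shelf lesion.**

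- Probable read as written: positive in the primary outcome.
- Probable taken as the Suspected list: fails the 1.5 mm floor, so not Probable. It still meets single criteria, so it is not literally Not CaW either.
- Probable taken as the Definite list (the top of the scale in Sections 8, 9, 11 and 12): fails the 2.0 mm floor, and again is not literally Not CaW.
- Not CaW also read as failing every category's full list: under either of the last two mappings the lesion becomes a clean negative.

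The protocol states none of these mappings.

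**4. Sensitivity of the estimate.** Eight extra positives are 8/753 = 1.06%, against a planned precision of 1 point. Let x be the share of web-free participants with a sub-threshold lesion called Probable. The documents give no value for x, so it is an assumption shown over a range. Apparent prevalence = 0.02 + x × 0.98.

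| Assumed x | Apparent prevalence | Positives in 753 |
|---|---|---|
| 0.5% | 2.5% | 18.7 |
| 1% | 3.0% | 22.4 |
| 2% | 4.0% | 29.8 |
| 5% | 6.9% | 52.0 |

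**5. Uncategorised lesions, if they were dropped from the denominator.** From 15/753 = 1.99%, dropping 8 scans gives 15/745 = 2.01%, and dropping 38 gives 15/715 = 2.10%.

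**The case against.** The strongest reply is that the second Section 7 reads like a template that relies on criteria set elsewhere. On that view Probable is shorthand for one of the lists in the first Section 7, and Not CaW means that no list is satisfied. The 1.0 mm lesion is then simply negative. This is a plausible intention, but the text does not state it, and a CRF that computes the category from single criterion boxes points towards the literal rule. Two blinded readers with a third to resolve discrepancies reduce the reliance on the computed field, but they work to the same rubric. SOP finalisation and a 50-scan pilot to confirm the criteria, both planned before enrolment, give an opportunity to settle the matter.

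Two stronger readings are tempting and are not supported.

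- A reader might infer that plaques, diaphragms and flaps fall out of the denominator and inflate prevalence, because Section 12 says "use complete-case for primary prevalence". But Section 11 sets the denominator as all participants with a diagnostic scan, and the second Section 7 judges scans by quality grade. Nothing says that a good scan showing a non-web lesion is treated as missing. Even if it were, the shift is to 2.10% at most over the range shown. Sections 8 and 9 also use absent as the negative level, which could hold such lesions.
- A reader might infer that the problem exists whatever the tiers are called. It does not: inflation of the primary numerator arises only if Probable is taken as written. Under the other two mappings the size floors apply, and what remains is a gap in the negative category.

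It is also fair to say that the prevalences in the first table of results only restate the assumed x.

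**Conclusion.** The point holds as a conflict between two stated rules. The second Section 7 gives Probable neither a number of criteria nor a size floor, and restricts Not CaW to lesions meeting no criterion. The first sets 1.5 mm plus a shape criterion even for Suspected. Unless Probable is meant to be the Suspected or the Definite list, sub-threshold lesions enter the primary numerator. Non-web lesions have no defined category: Possible is undefined and counts as positive in a sensitivity analysis, so it is not a proper place for a plaque or flap.

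The estimate is sensitive because few cases are expected: about eight sub-threshold calls equal the whole planned precision. Whether eight would occur cannot be derived from the documents, so no actual inflation is claimed. The part about non-web lesions is a defect in the category algorithm, with little effect on the estimate. The sample size calculation is not affected. The wording should be corrected before the central reads.

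**What to change.** Reconcile the two Section 7 texts before the central reads scheduled for May to June 2026, and preferably before enrolment.

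1. State which criteria list of the first Section 7, with its own size floor, each of Definite, Probable and Possible corresponds to. Which floor applies to the primary outcome is for the investigators to decide.
2. Redefine Not CaW as: does not satisfy the full criteria list of any web category, or is ruled out by an exclusion as finally reconciled.
3. Reconcile the exclusions. In particular, settle whether plaque excludes only when it lies in the posterior wall, as in the first text, or anywhere, as the second text could be read. Otherwise a web with plaque on another wall has no clear call.
4. Program the CRF so that every Grade 1–2 scan receives exactly one category.
5. State that non-web lesions on diagnostic scans count as negative and stay in the Section 11 denominator.

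The cost is wording and one CRF rule, with no added participants or scans. The downside is that the reported prevalence may be slightly lower than under the literal Probable rule.

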- Pre-specified imaging protocol; machine presets harmonized across sites.
- Central training and periodic re-calibration; quarterly site audits of randomly selected studies.
- Consecutive sampling within clusters to reduce selection bias; track response rates.
- Maintain blinding; lock image sets before adjudication.

14) Ethics and Safety

- Minimal-risk imaging study; no ionizing radiation in the primary protocol.
- Informed consent; separate consent for optional CTA.
- Participants with **incidental significant carotid stenosis** or suspected thrombus receive counseling and referral per local care pathways.
- Data privacy per GDPR; coded IDs; secure storage.

15) Feasibility & Timeline

- **July-December 2025:** Finalize SOPs, train sonographers, pilot 50 scans to confirm criteria and quality metrics.
- **January 2026 – June 2026:** Enrollment and scanning.
- **May – June 2026:** Central reads and adjudication.
- **July – December 2026:** Analysis, manuscript preparation.

16) Case Report Forms (CRFs) — Core Fields (summary)

- **CRF-1 (Eligibility & Consent).**
- **CRF-2 (Demographics/Risk).**
- **CRF-3 (Ultrasound Acquisition):** device, probe, settings, windows obtained, quality.

- **CRF-4 (Ultrasound Findings):** CaW category; measurements; Doppler velocities; plaque; stenosis category; images saved (IDs).
- **CRF-5 (Adjudication):** reader A/B calls; consensus; κ .
- **CRF-6 (Validation Substudy):** CTA done (Y/N), CTA result (CaW Y/N), discordance reason.

17) Reporting

- Report per **STROBE**; include gallery of representative DUS images (longitudinal shelf-like lesion, transverse membrane, microflow swirl) and a flow diagram. Explicitly discuss limitations: web detection is operator-dependent; ultrasound criteria are less standardized than CTA; very low prevalence may limit precision without large samples.

Key References (for protocol justification)

1. **Fontaine L, et al.** *Ultrasound characteristics of carotid web*. J Neuroimaging. 2022. Describes B-mode/Doppler appearances; microflow imaging improves detection. ([PMC](#), [PubMed](#))
2. **Chen H, et al.** *Carotid webs: pathophysiology, diagnostic approaches, and management*. J NeuroIntervent Surg. 2024. Overview; ultrasound visualization best in longitudinal B-mode. ([jn.is.bmj.com](#))
3. **Radiopaedia (review).** *Carotid web*. Emphasizes shelf-like defect at posterior ICA bulb and CTA reference standard. ([Radiopaedia](#))

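### Reader blinding does not cover the operator's marks or category, although caliper-marked stills are mandatory, so the independence of the central read is not protected

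*Protocol*

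**What the plan says.** **Images.** The per-side acquisition minimums in Section 7 of the protocol (Sonographic Case Definition) include still frames "with calipers for all measurements". The morphologic measurements listed in the same section are web thickness, web length or projection, projection angle and distance from the flow divider. The CRF add-ons require "Mandatory image IDs linked to each measurement".

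**Other stored material.** Section 6 also makes cine loops in both planes mandatory, with stills with and without colour. It sets no caliper requirement for these.

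**Blinding.** Section 8 says that "central readers (two expert neurosonologists) are blinded to site and each other". The same bullet keeps clinical data other than age and sex from the operators; for the readers it names only site and the other reader. Section 7 adds "Two blinded readers score Definite/Probable/Possible/Not CaW; discrepancies resolved by third reader under the same rubric". Section 13 adds "Maintain blinding; lock image sets before adjudication".

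**Records.** Section 16 places the operator's category and measurements on CRF-4 and the reader calls on CRF-5.

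**The concern.** Section 3 describes the design as a survey with blinded central adjudication of images, and inter-observer agreement is both a secondary objective and a secondary outcome. Section 17 concedes that detecting a web depends on the operator, which is what an independent central read is there to address.

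Calipers on a still tell a reader that the operator found something worth measuring, and where. If both readers receive that frame, they share a cue that does not come from their own reading. Three results are then exposed:

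- **Kappa** can rise because both readers lean on the same mark.
- **ICC** on frames that already carry calipers is not an independent remeasurement.
- **Adjudicated prevalence** can move toward the operator's call.

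The per-reader sensitivity analysis in Section 12 would not reveal this, because each reader would carry the same cue.

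**Working it through.** **1. What the text allows.**

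| Question | What the protocol gives |
|---|---|
| Are caliper stills stored? | Yes, as a per-side minimum (Section 7) |
| Are readers blinded to the operator's category, measurements or marks? | Not listed; only site and the other reader (Section 8) |
| Does locking the image sets help? | It fixes the content; nothing says annotations are removed (Section 13) |
| Which images or forms do readers receive? | Not stated |
| Is there material without a caliper requirement? | Yes, cine loops and stills with and without colour (Section 6) |

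Exposure is therefore neither prescribed nor prevented.

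**2. The plan's own figures.** Section 5: 1.96² × 0.02 × 0.98 / 0.01² = 752.95, rounded up to 753; 753 × 1.10 = 828.3, rounded up to 829. Both reproduce, and neither depends on this point. The 10% re-read sample is then about 75 to 83 people. Expected webs: 75 × 0.02 = 1.5 and 83 × 0.02 = 1.66. The chance that such a sample holds no web at all is 0.98^75 = 0.22 or 0.98^83 = 0.19, ignoring clustering.

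**3. Direction and possible size of the effect on kappa.** The protocol gives no reader accuracy, operator accuracy or rate of following a cue, so all three are assumptions. Calls are reduced to web or no web.

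- True status t has prevalence 0.02. The operator's call is o (1 or 0).
- Each reader adopts o with probability c and otherwise reads independently given t. The chance of a positive read is q = (1 − c)·r + c·o, where r = Se if a web is present and r = 1 − Sp if not.
- With w the probability of each (t, o) cell: m = Σ w·q, P11 = Σ w·q², kappa = (P11 − m²)/(m − m²).

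Take reader Se 0.70 and Sp 0.99, operator Se 0.80 and Sp 0.98.

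*c = 0:* m = 0.02 × 0.70 + 0.98 × 0.01 = 0.0238; P11 = 0.02 × 0.49 + 0.98 × 0.0001 = 0.009898; kappa = (0.009898 − 0.000566)/(0.0238 − 0.000566) = 0.40.

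*c = 0.50:*

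| Cell | w | q | w·q | w·q² |
|---|---|---|---|---|
| web, operator positive | 0.0160 | 0.850 | 0.013600 | 0.011560 |
| web, operator negative | 0.0040 | 0.350 | 0.001400 | 0.000490 |
| no web, operator positive | 0.0196 | 0.505 | 0.009898 | 0.004998 |
| no web, operator negative | 0.9604 | 0.005 | 0.004802 | 0.000024 |

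m = 0.0297; P11 = 0.01707; kappa = (0.01707 − 0.00088)/(0.0297 − 0.00088) = 0.56.

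| c | kappa | Each reader's positive rate |
|---|---|---|
| 0 | 0.402 | 2.4% |
| 0.10 | 0.402 | 2.5% |
| 0.25 | 0.436 | 2.7% |
| 0.50 | 0.562 | 3.0% |
| 0.75 | 0.755 | 3.3% |

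**4. Same calculation with operator accuracy equal to reader accuracy.** Each reader's accuracy then stays the same at every c, so any rise in kappa is spurious agreement.

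| Se / Sp | c = 0 | c = 0.10 | c = 0.25 | c = 0.50 |
|---|---|---|---|---|
| 0.70 / 0.98 | 0.279 | 0.286 | 0.324 | 0.459 |
| 0.80 / 0.99 | 0.487 | 0.492 | 0.519 | 0.615 |
| 0.90 / 0.995 | 0.702 | 0.705 | 0.720 | 0.776 |

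Here the positive rate does not change with c. The rise in step 3 comes from assuming an operator who calls more positives than the readers, so the pull on prevalence depends on how far operator and readers differ.

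**The case against.** A reader might infer that both readers do see the operator's call and that agreement is therefore inflated. The documents do not support that:

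- **The reading package is not described.** The caliper line is an acquisition rule. Nothing hands the marked frames or CRF-4 to the readers, and the operator's category and the reader calls sit on separate forms.
- **A caliper is not a category.** The definitions in Section 7 use a maximal length, a minimal width and the relation between the two, so a lesion must be measured to rule a web out as well as in. Plaque descriptors and a stenosis category are also recorded. A mark shows that a structure was measured, not that it was called a web.
- **Material without a caliper requirement is already mandatory.** The cine loops that readers would need are stored.
- **Independence is the evident intent.** The protocol calls the adjudication and the readers blinded, and the procedures were still to be finalised during set-up (Section 15). Details of a reading package often sit there.
- **The kappa figures are not the trial's.** A kappa of 0.76 requires expert readers to follow the cue in three quarters of reads, and at one tenth the shift is negligible. With one or two expected webs, sampling error in kappa far exceeds a shift of a few hundredths.

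All of this limits the certainty and size of the effect. What remains is that the protocol does not leave the scope of reader blinding open: Section 8 states it, and the stated scope omits the operator's findings. The general words about blinding do not widen it, and clean frames remove no cue if marked frames travel with them. Once the reads are made, no analysis can restore independence.

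**Conclusion.** The point holds as a gap in protection, not as a demonstrated bias. The protocol requires caliper-marked stills and blinds the readers only to site and each other, so nothing prevents a shared operator cue from reaching both.

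If it does, the expected direction is upward for kappa and ICC, and toward the operator's call for prevalence. The size cannot be derived from the document. Under the first set of assumptions, kappa rises by 0.034 (0.40 to 0.44 when rounded) if 25% of reads follow the cue and by 0.16 if 50% do. At 10% the rise is under 0.01 in every scenario tried. These figures rest wholly on assumed accuracies, an assumed rate of following the cue and a two-category call. The sample size is unaffected. This is a cheap improvement.

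**What to change.** In Sections 6 to 8 of the protocol:

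1. Store an unannotated copy of every still that carries calipers.
2. Have readers score the category from the cine loops and unannotated stills, and take their own measurements.
3. Release caliper frames only after both readers' calls are locked.
4. Extend the reader-blinding line to the operator's category, the operator's measurements and annotations, and participant clinical data.

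The cost is one extra saved frame per measurement and a filter on the reading package, with no extra reader or participant. The clean copy has to be saved at acquisition, so the change is best made before scanning starts (January 2026 in Section 15). One limit remains: the operator still chooses the frozen plane, so even a clean still can hint at suspicion. The mandatory cine loops should therefore be the main basis for the category.

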- Prior carotid endarterectomy/stenting, neck irradiation, or known vasculopathy with non-web lesions that preclude assessment.
- Inadequate acoustic window despite optimization (these participants contribute to feasibility metrics, not prevalence numerator/denominator).

Setting & sampling frame

- Community-based recruitment (secondary schools / universities).

- Stratified cluster sampling by sex, age bands (15-17, 18–21, 22–25), and recruitment site to approximate the underlying population.

5) Sample Size

Assumptions

- Expected prevalence $p=0.02$ (2%)
- Desired absolute precision $d=0.01$ ($\pm 1\%$)
- Confidence level 95% $\rightarrow Z=1.96$

Formula

$$n = \frac{Z^2 p(1-p)}{d^2} = \frac{1.96^2 \times 0.02 \times 0.98}{0.01^2} = 752.95$$

$$\frac{1.96^2 \times 0.02 \times 0.98}{0.01^2} = 752.95$$

Required minimum sample size: 753 participants (round up) plus 10% for non-diagnostic/poor-quality scans and no-shows, i.e. **totally 829 participants is needed to screen.**

6) Ultrasound Acquisition Protocol

Equipment & presets

- High-end ultrasound suplex machine Canon Aplio a-series with B-mode, color/power Doppler, spectral Doppler, and microflow/superb microvascular imaging. High-frequency linear transducer PLT-1005BT (5–14 MHz).
- Patient supine, slight neck extension/contralateral head rotation; optimize for the carotid bulb/ICA origin.

Scanning sequence (bilateral)

1. **B-mode:** transverse sweep from distal CCA through bulb into proximal ICA and ECA; then longitudinal (anterolateral, lateral, posterolateral windows).
2. **Color Doppler:** at low PRF to visualize flow separation/recirculation; adjust wall filter and gain to avoid overwriting thin intraluminal structures.
3. **Spectral Doppler:** with angle correction $\leq 60^\circ$, sample volume 1.5–2.0 mm; measure PSV and EDV in standard segments (distal CCA, bulb, proximal ICA).

4. **Microflow imaging:** focused on the posterolateral bulb to delineate thin shelf/membrane and adjacent flow.

Image storage

- Mandatory cine loops (≥ 3 cardiac cycles) in longitudinal and transverse of the bulb/ICA origin, plus still frames with and without color, and spectral Doppler waveforms with angle annotation ((same as in protocol of ANTIQUE study).
- Label side and projection; record machine make/model, probe, presets.

7) Sonographic Definition of Carotid Web

Definite carotid web:

Inclusion criteria:

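### Section 8 bases inter-observer agreement on a 10% random re-read holding about 1.5 expected webs, while the routine paired reader calls recorded on CRF-5 would give a usable kappa

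*Protocol*

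**What the plan says.** Protocol section 2 lists inter-observer agreement for web detection as a secondary objective, and section 11 lists agreement metrics as a secondary outcome. Section 8 (Reliability) names the data source: a "10% random sample re-read for inter-observer agreement", with Cohen's kappa for categorical calls and an ICC for continuous measures. The reader guidance in the second section 7 (Sonographic Case Definition) also plans 10% repeat reads for kappa and ICC, but does not say whether these are between or within readers. Section 12 specifies kappa with a 95% CI and "ICC(2,1) for continuous measures", and ties neither to the 10% sample.

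Four other provisions describe routine double reading:

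- Section 7, reader guidance: "Two blinded readers score Definite/Probable/Possible/Not CaW; discrepancies resolved by third reader under the same rubric". No restriction to a subset is given.
- Section 8, Blinding: the two central readers are blinded to each other.
- Section 16, CRF-5: the form records "reader A/B calls; consensus", and the same line then lists kappa.
- Section 12, sensitivity analysis (iii): prevalence is also to be estimated separately for each reader.

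**The concern.** A random 10% of a survey planned around a 2% condition contains hardly any positives, and kappa for a rare finding is driven by the positives. Web thickness, length and projection angle can be compared only where both readers saw and measured a web. The agreement objective therefore rests on one or two lesions, while the routine reads appear to supply independent paired calls on ten times as many scans.

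At stake is the study's evidence on reader dependence of the finding it counts. Section 17 names operator-dependence of web detection among the limitations to be discussed. A kappa interval from about 0 to 1 could not separate chance agreement from perfect agreement.

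**Working it through.** **Inputs from the protocol.** Section 5: prevalence 0.02, absolute precision 0.01, Z = 1.96, and "Required minimum sample size: 753 participants (round up) plus 10% for non-diagnostic/poor-quality scans and no-shows", giving 829 to screen. Section 8: 10% random re-read, with no enrichment for webs. The protocol gives no true kappa, so 0.6, 0.7 and 0.8 are assumed.

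**1. The plan's own figure.** n = 1.96² × 0.02 × 0.98 / 0.01² = 752.95, rounded up to 753. 753 × 1.10 = 828.3, rounded up to 829. Both are reproduced.

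**2. Webs in the re-read sample.** 10% of 753 is 75 scans; 10% of 829 is 83. Counting one scan per participant:

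- 75 scans: 75 × 0.02 = 1.5 expected. P(0) = 0.98^75 = 0.22. P(at most 1) = 0.98^75 + 75 × 0.02 × 0.98^74 = 0.56. P(5 or more) = 0.017.
- 83 scans: 1.66 expected. P(0) = 0.19, P(at most 1) = 0.50.

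Over a range of prevalence, with 75 scans:

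| Prevalence | Expected webs | P(0) | P(at most 1) |
|---|---|---|---|
| 0.5% | 0.4 | 0.69 | 0.95 |
| 1% | 0.75 | 0.47 | 0.83 |
| 2% | 1.5 | 0.22 | 0.56 |
| 4% (assumed, if looser categories count) | 3.0 | 0.05 | 0.19 |

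**3. Kappa.** Take two readers, each calling p = 2% positive, with true kappa k. The cell probabilities are:

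- both positive: a = p² + k·p(1−p)
- each discordant cell: b = p(1−p)(1−k)
- both negative: 1 − a − 2b

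At k = 0.70, a = 0.0004 + 0.70 × 0.0196 = 0.01412, b = 0.0196 × 0.30 = 0.00588, and both negative = 0.97412. Kappa is undefined when every scan is called negative by both readers: 0.97412^75 = 0.14.

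Large-sample variance: (1−k)/n × [(1−k)(1−2k) + k(2−k)/(2p(1−p))]. At k = 0.70 the bracket is −0.12 + 0.91/0.0392 = 23.09.

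- n = 75: SE = √(0.30 × 23.09/75) = 0.304, half-width 1.96 × 0.304 = 0.60.
- n = 753: SE = √(0.30 × 23.09/753) = 0.096, half-width 0.19.

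The normal approximation is poor at n = 75, so 200,000 simulated tables per setting give the sampling ranges (central 95%, among tables where kappa is defined):

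| True kappa | n = 75: undefined | n = 75: undefined or ≤ 0 | n = 75: range | n = 753: range |
|---|---|---|---|---|
| 0.6 | 12% | 40% | −0.02 to 1.00 | 0.35 to 0.79 |
| 0.7 | 14% | 34% | −0.01 to 1.00 | 0.47 to 0.87 |
| 0.8 | 16% | 30% | 0.00 to 1.00 | 0.60 to 0.94 |

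At n = 753 the simulated share of undefined kappas was 0.0.

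**4. ICC for web dimensions.** This needs at least two lesions measured by both readers. At k = 0.70 the expected number of scans called positive by both is 75 × 0.01412 = 1.06 in the re-read and 753 × 0.01412 = 10.6 in the full set. In 75 scans, P(at most one such scan) = 0.98588^75 + 75 × 0.01412 × 0.98588^74 = 0.34 + 0.37 = 0.71.

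The full set does not make this ICC precise. With 11 lesions, two readers, an assumed ICC of 0.70 and no systematic reader difference, F = 1.70/0.30 = 5.67. With the 97.5% F quantile on 10 and 10 degrees of freedom (3.72), the limits are (5.67/3.72 − 1)/(5.67/3.72 + 1) = 0.21 and (5.67 × 3.72 − 1)/(5.67 × 3.72 + 1) = 0.91.

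**The case against.** The best defence is that the protocol already provides for the better analysis. CRF-5 lists kappa on the form that holds the routine reader calls, section 12 does not tie kappa to the 10% sample, and section 7 does not say that its repeat reads are between readers. The 10% may have been meant for repeatability within a reader. This stands in part: it turns the point into a conflict between section 8 and CRF-5. It does not remove it, because section 8 expressly assigns the random re-read to inter-observer agreement.

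Several stronger readings are tempting, and the document does not support them:

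- *Every scan is stated to be double read.* It is not. Unrestricted two-reader scoring, third-reader adjudication, CRF-5 and the per-reader estimates together imply it.
- *Kappa and ICC will all fail.* Undefined kappa is a 12% to 16% risk; the usual outcome is an uninformative value. At 2% prevalence, 44% of samples of 75 hold two or more webs, so a web-dimension ICC is sometimes computable. Velocities exist for every participant, and their ICCs could be estimated from about 75 scans if re-measured.
- *A re-read can only measure intra-observer repeatability.* A re-read by another observer is inter-observer. The weakness is the size and random selection of the sample.
- *The repair is free throughout.* CRF-5 lists calls; measurements sit on CRF-4. Nothing shows that both central readers' measurements are kept.
- *Operator-dependence is the main limitation.* Section 17 lists it with others and does not rank them.

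It is also fair to say that the calculation is binary, whereas the readers use four categories and the suspected-web criteria are looser. More positive calls would help, but an assumed 4% still gives only 3 in 75.

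**Conclusion.** The point holds. As section 8 is written, kappa for web detection would come from about 75 scans with 1.5 expected webs and would range from about 0 to 1. The web-dimension ICC would often not be computable and would otherwise be very imprecise. This rests on the protocol's 2% prevalence, equal reader marginals and an assumed true kappa of 0.6 to 0.8; the conclusion for kappa does not change across that span or at any prevalence from 0.5% to 4%.

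The paired pre-adjudication calls, which the protocol implies for all scans, hold about 15 webs (753 × 0.02 = 15.1) and give a kappa range of about 0.47 to 0.87 at a true value of 0.70. If prevalence is lower, the full set thins too: 7.5 expected webs at 1% and 3.8 at 0.5%. The web-dimension ICC stays imprecise even with all lesions. The damage is confined to the agreement objective; the primary prevalence estimate is unaffected.

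**What to change.** Before central reads begin:

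- State in section 8, and in the matching line of section 7, that both readers call every scan, and that inter-observer kappa with its 95% CI is computed from the independent reader A and reader B calls before adjudication, on all scans. Report positive and negative agreement beside it, because kappa alone is unstable at 2% prevalence. This agrees with the kappa field on CRF-5.
- Compute the ICC for web dimensions from all lesions measured by both readers, and say in advance that about 11 are expected, so that the interval will be wide.
- If the 10% re-read is kept, label it intra-observer. It could then be reported as a supplement, since section 2 names only inter-observer agreement.

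Cost: if both readers do call every scan, the kappa change needs no extra reads. The ICC change needs fields on CRF-5 for each reader's lesion measurements, and both readers must measure each lesion they call, which at this prevalence is a small number of scans.
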